4.1.2.1 Dose-Limiting Toxicities

For the purpose of this study, a DLT will be defined as any of the following events occurring during the DLT window and not attributable to underlying disease or intercurrent illness:

- Hematological toxicities defined as:
 - [REDACTED]
 - [REDACTED]
 - [REDACTED]
 - [REDACTED]
 - [REDACTED]
- Any non-hematological toxicities Grade ≥ 3 except for:
 - [REDACTED]
 - [REDACTED]

- [REDACTED]
- [REDACTED]
- [REDACTED]
- [REDACTED]
- [REDACTED]
- [REDACTED]
- [REDACTED]
- [REDACTED]
- [REDACTED]
- Additional DLTs not fulfilling the above criteria
 - [REDACTED]

During the dose escalation phase, participants who withdraw before the end of the DLT period, and participants who did not receive two doses of RO7296682 in combination with atezolizumab for reasons other than DLTs, will be replaced to ensure that at least 3 DLT evaluable participants have been assessed prior to moving to the next dose level (see Section 7 for replacement rules). The DLT will be counted for each dose separately and each participant will contribute one single representative data point to the EWOC design.

4.1.2.2 Individual Dose Increase for Participants in a Dose-Escalation Cohort (Part I)

At the discretion of the Investigator and in agreement with the Sponsor, intra-participant dose escalation for individual participants treated at lower RO7296682 doses may be considered for treatment at higher doses of RO7296682 than those allocated at the time of enrollment, if the doses are considered safe. Thus, after completing at least 9 weeks on treatment or after the first tumor assessment, whichever comes first, at one dose level with no major safety concerns, a participant may receive a higher RO7296682 dose level at the next scheduled cycle within the participant's dosing schedule, which is at least one dose level below the highest currently evaluated dose or up to the MTD and/or the RP2D of RO7296682, if reached. If intra-participant dose escalation for an individual participant is considered, treatment must be administered as indicated in Section 6.1.1

as if it was the first administration to the study participant (i.e., 4-hour infusion for the first higher dose of RO7296682).

4.1.3 Stopping Rules Criteria for Dose-Escalation

Built-in safety constraints are in place in the dose-escalation process to prevent exposing participants to undue risk of toxicity. The mCRM with EWOC will propose to stop the dose-escalation under the following circumstances:

- [REDACTED]
- OR
- [REDACTED]
- OR
- [REDACTED]

Due to the exploratory nature of this study, any part of its conduct can be discontinued at any time at the discretion of the Sponsor. The Sponsor will notify the Investigators and Health Authorities if the study is discontinued or the development program is terminated.

4.1.4 Communication Strategy

Screening starts with the signature of the study Informed Consent Form (ICF). Patients should be formally screened in the study interactive (voice/web) response system (IxRS) as soon as consented, to allow for the assignment of a participant's screening ID. A participant is considered enrolled into the study when eligibility is confirmed by the investigational site and entered in the study IxRS system.

During the **dose escalation (Part I)**, information will be communicated, as follows:

- For all participants, during dose escalation Part I, it is anticipated that the Investigator(s) will inform the Sponsor that a participant has been dosed and provide a brief summary of the status of the participant in terms of safety and tolerability to RO7296682 in combination with atezolizumab.
- In the event of a DLT, the Investigator will contact the Sponsor immediately to discuss participant status and action taken/to be taken.
- The Sponsor will organize SDEC meetings with the Investigators to discuss the safety and tolerability of RO7296682 in combination with atezolizumab and the dose selected for the next cohort.

The SDEC meeting will be conducted prior to each dose-escalation, by teleconference, in presence of the Investigators, the Medical Monitor, the Sponsor Clinical Team, and any other person the Investigators consider necessary to assist with the decision. During each teleconference:

- National Cancer Institute common terminology criteria for adverse events (NCI-CTCAE [v5.0]) toxicities (see [Appendix 2](#)) will be discussed along with available PK, ADA, and PD data, in addition to safety laboratory results and any other available data that may assist the dose-escalation decision process.
- Dose escalation will only proceed to the next dose level if the Investigators and the Sponsor are satisfied with the safety profile of the previous cohort and agree to move to the next dose level.
- The dose level of RO7296682 will be approved during the SDEC meeting and documented in writing.

For Part II ongoing medical data review will be performed by the Sponsor together with the investigators.

- **For Part III** (Dose Expansion) accumulating clinical data review will be performed by an Internal Monitoring Committee (IMC). For details, see [Appendix 1](#), Section 3.3.

In addition to these communications, the Sponsor and Investigators will be in regular contact throughout the study by email/telephone/fax.

The Sponsor will be available 24 hours a day to discuss any medical or study-related issues that may arise during the conduct of this study.

4.2 SCIENTIFIC RATIONALE FOR STUDY DESIGN

4.2.1 Rationale for Study Population

Part I: In Part I, dose-escalation participants with advanced and/or metastatic NSCLC, MEL, HNSCC, OvCa, TNBC, and EsC tumors will be enrolled. The indication selection was based on internal prevalence analyses on FOXP3 expression in order to select tumor types that are expected to be most responsive to Treg depletion. For details of the analyses, refer to the [Investigator's Brochure](#).

Part II: For signal seeking purposes, Part II was designed to include tumor types and patient characteristics that are most likely to derive clinical benefit from Treg depletion (through RO7296682) and from checkpoint inhibition (through atezolizumab). In-house analysis of tumor samples (archival and fresh biopsy) have shown a strong correlation of

(as defined by [REDACTED]) and [REDACTED] [REDACTED]. To this end, Part II will include participants with

NSCLC, MEL, and HNSCC who present with an [REDACTED] (see Section 5.1, [REDACTED]). In addition, Part II participants must have experienced initial benefit from PD-1/PD-L1 treatment before they ultimately progressed (acquired resistance; see Section 5.1). It has been suggested that upon PD-1/PD-L1 treatment Tregs express PD-1 at equivalent levels as CD8+ or CD4+ effector/memory T cells,

thereby enhancing the Treg proliferation and suppressive function (Wang et al 2020, Kamada et al 2019). The requirement of initial benefit was incorporated in order to rule out primary resistance towards checkpoint inhibition.

Part III: Part III is designed to further explore signals (i.e., clinical benefit) that were generated from this or the single agent WP41188 study and/or based on emerging treatment landscapes affecting the SoC in a particular indication (e.g., chemotherapy in addition to checkpoint blockade as part of the SoC treatment). Enrollment of participants in tumor-specific cohorts may be triggered provided the gating criteria in Section 9.5 have been met. The tumor-specific cohorts will enable further investigation of clinical benefit in a less restrictive population by removing the [REDACTED] or acquired CPI-resistance criteria required in Part II. In the current protocol, the specifics for the NSCLC, HNSCC, and MEL cohorts have been outlined in [Appendix 6](#), [Appendix 7](#) and [Appendix 8](#). Should the emerging data suggest that other indications, patient characteristics, or drug combinations warrant further investigation, a new cohort will be opened through a protocol amendment, addressing also the needs of a potential safety run-in/dose escalation phase with additional treatments like SoC chemotherapy ([Appendix 9](#)).

4.2.2 Rationale for the mCRM-EWOC Design

Part I dose escalation will be carried out according to a mCRM-EWOC design and based on the occurrence of DLTs. The mCRM-EWOC design has many favorable characteristics:

- It adaptively fits a dose DLT response curve by incorporating toxicity data from eligible participants among different cohorts, and preclinical or clinical information from compounds with similar modes of action via the prior.
- The design also locates the MTD more efficiently, without pre-specifying exact dose levels for each cohort. Dose selections are made based on the DLT dose response curve measured by a 2 parameter logistic model over the dose range, subject to clinical judgment and mandated safety constraints that limit the size of dose increments. Moreover, the EWOC algorithm highly reduces risks of exposing participants to overly toxic doses. Of note, the model provides only the upper limit for recommended dose. A dose lower or higher than the model recommended dose may be selected based on clinical judgment.

4.2.3 Rationale for Biomarker Assessments

According to the mode of action of RO7296682, depletion of Tregs will lead to reinvigoration of the anti-tumor immune response in the TME. As such, the goal of the biomarker assessments is to confirm the RO7296682 mode of action at the tumor site, when administered in combination with atezolizumab, and establish a dose-response relationship.

In-house tumor sample analyses and real world data have shown a strong correlation of [REDACTED] and [REDACTED]. Therefore, archival tumor samples will be collected at screening from all participants enrolled in the study and analyzed for immune-phenotype and immune contexture in all parts of the study. In order to test the effect of the treatment in a patient population that could benefit the most from the therapy, Part II of the study will enroll only participants with [REDACTED] as assessed by prospectively characterizing the tumor immune-phenotype on the archival tissue.

Treatment-induced intra-tumoral PD changes will be assessed by examining alterations in the number, activation/differentiation status, and location of intra-tumoral residing immune cells. In particular, a reduction of Tregs and/or an increase in Teff/Treg is expected. This will be monitored closely in all samples. Moreover, the expression of tumor markers (including but not limited to PD-L1) associated with response to RO7296682 will be examined. These changes will be assessed in mandatory, fresh, paired tumor biopsy samples collected from participants enrolled in Parts II and III.

RO7296682 treatment may result in changes in peripheral blood immune cells and soluble circulating markers such as cytokines or tumor markers. Hence, in all parts of the study, plasma samples will be analyzed with respect to the presence or changes in levels of cytokines, inflammation, and soluble tumor markers that may be associated with treatment benefits. Moreover, blood samples will be assessed with respect to alterations of immune cells in their absolute counts and activation/differentiation status as well as their functional capacity following treatment with RO7296682. Receptor occupancy (RO) assessments following treatment with RO7296682 in combination with atezolizumab will also be undertaken to evaluate the degree of target binding of RO7296682 (in association with PK) in Part I only.

Finally, in order to evaluate the value of circulating tumor DNA (ctDNA) as a response predictor to RO7296682 in combination with Atezolizumab, the dynamics of plasma ctDNA will be analyzed in relation to tumor size variations and response to treatment. Changes in ctDNA level will be assessed in samples collected in Parts II and III of the study.

In order to determine if and by how much RO7296682 in combination with atezolizumab affects Treg homeostasis in the immune contexture of healthy tissue, mandatory healthy skin punch biopsies will be collected at baseline and on treatment, at the same time points as the mandatory tumor biopsies. It is expected that analyses from such healthy tissues could provide critical information regarding a differential between numbers of activated Treg in the tumor and the non-activated Treg in the healthy tissue.

If preliminary data suggest that modification of the on-treatment tumor biopsy or healthy skin punch biopsy time point would be appropriate, alternative on-treatment biopsy time-points may be considered.

Optional tumor and/or healthy tissue biopsies may be taken at any time point and in all parts of the study (Parts I-III), for example, due to either skin-related AEs, disease progression, or long-lasting stable disease (SD) as per Investigator discretion and if the participant consents to these samples being taken to aid the understanding of immune resistance or homeostasis mechanisms.

Finally, all specimens will be used also for research purposes to identify additional biomarkers that may be useful to predict and monitor response to RO7296682 in combination with atezolizumab and safety, assess PD effects of RO7296682 in combination with atezolizumab, and investigate any mechanisms of resistance to therapy. Additional biomarkers may be measured if initial data lead to strong scientific rationale for these measurements.

4.2.4 Rationale for Real wOrld PROgnostic Score

The Real wOrld PROgnostic (ROPRO) score serves as an objective tool to assess the patient's life expectancy and has been shown to enable prognosis of OS homogeneously across solid cancer indications ([Becker et al. 2020](#)). The ROPRO score consists of routinely collected clinical parameters (listed in Section [8.2.10](#)) reflecting both the tumor biology and patient characteristics. It has been shown to strongly outperform other risk scores, such as the Royal Marsden Hospital Score. Patients with elevated ROPRO scores (upper 10%) had a 7.91-fold (95% confidence interval [CI] 7.45–8.39) increased death hazard compared with that of patients with low scores (lower 10%). Refer to [Appendix 10](#) for data demonstrating that a poor ROPRO score correlates with reduced probability of 12-week survival.

In this study, the ROPRO score serves to objectively support the Investigator with the assessment of the commonly used inclusion criteria "Life expectancy, in the opinion of the Investigator, of ≥ 12 weeks" (see Section [5.1](#)). Patients who demonstrate a poor ROPRO score, should be excluded unless clinical judgment may determine potential clinical benefit and thereby the inclusion of the patient in the study. Such decisions will be clearly documented.

4.2.5 Rationale for Optional Stool Sample Collection

The gut microbiome has been shown to be a key determinant of immune regulation in cancer, in part by influencing T-cell driven anti-tumor responses ([Routy et al. 2018](#)). For example, antibiotic treatment is associated with poor survival outcomes to anti-PD-1 therapy in NSCLC, renal cell carcinoma, and urothelial carcinoma (UC) ([Elkrief et al. 2019](#)). Conversely, the risk of colitis with CITs may be predicted on the basis of a patient's pretreatment microbiome ([Dubin et al. 2016](#); [Chaput et al. 2017](#)). In addition, the role of Tregs in influencing the progression of inflammatory bowel disease and the development of colorectal cancer has been established in the literature ([van Herk et al. 2016](#); [Neurath 2020](#)). Thus, heterogeneity in microbiome composition across patients may be a relevant driver of safety events, in addition to efficacy.

This study will examine a participant's microbiome at baseline and on-treatment in order to investigate potential changes by RO7296682 in combination with atezolizumab.

4.3 JUSTIFICATION FOR DOSE

4.3.1 Rationale for Dosage Selection of Atezolizumab

Atezolizumab is approved for the treatment of patients with locally advanced or metastatic UC and those with metastatic NSCLC who have disease progression during or following platinum-containing chemotherapy at a dose of 1200 mg as an intravenous infusion over 60 minutes every 3 weeks (Q3W) until disease progression or unacceptable toxicity. If the first infusion is tolerated, all subsequent infusions may be delivered over 30 minutes.

4.3.2 Rationale for Dosage Selection of RO7296682

The starting dose and regimen of RO7296682 in combination with atezolizumab is defined as [REDACTED] mg administered Q3W by IV administration. The RO7296682 starting dose and schedule were selected based on several factors, including non-clinical toxicology, exposure and efficacy studies of RO7296682 and clinical experience from RO7296682 administered as a single agent in study WP41188:

Non-clinical toxicology data

RO7296682 was tested in combination with atezolizumab in a whole blood assay to investigate the potential of the combination to trigger systemic cytokine release. When compared with single agent RO7296682 in the same assay, [REDACTED] [REDACTED] Therefore, at the starting dose of [REDACTED] mg for RO7296682 combined with atezolizumab at the dose of [REDACTED] mg, [REDACTED] [REDACTED] after the IV administration. In addition, the combination of atezolizumab and RO7296682 was tested in mouse models for efficacy assessment. [REDACTED] were reported in these pharmacological models.

Clinical data from single agent study WP41188

RO7296682 is being investigated as a single agent in the ongoing WP41188 Phase I study. At the time of clinical cutoff date 10 June 2020 (in order to produce validated safety outputs), 21 participants had received multiple ascending doses of RO7296682 up to [REDACTED] mg on a Q3W schedule and had not shown any dose limiting toxicity event. The safety profile, PK, and immune-related PD effects in the peripheral blood were analyzed to define the starting dose in this study.

At the time of finalizing the first version of this protocol, the highest cleared dose of RO7296682 in the ongoing WP41188 study was [REDACTED] mg [REDACTED]. Further dose increments will be explored in the WP41188 study until MTD or optimal biological dose is reached.

Based on the clinical experience from study WP41188, the selected RO7296682 starting dose of [REDACTED] mg is expected to be safe and result in exposure levels that will initiate no or minimal PD response, either from a [REDACTED] or from a [REDACTED] [REDACTED]. Indeed, starting at [REDACTED], a consistent PD response is observed with a [REDACTED]

Analyzing the RO7296682 PK data at doses from [REDACTED] to [REDACTED] mg [REDACTED], preliminary exposure estimates [REDACTED]

Given the preliminary data, RO7296682 PK is considered [REDACTED] and shows [REDACTED]

Given the risk for overlapping toxicities between an anti-CD25 agent and a CPI targeting the PD-1/L1 pathway (see [Investigator's Brochure](#)), the proposal of a known safe starting dose of RO7296682 [REDACTED] mg is considered adequate for the initiation of the study.

4.3.2.1 Definition of Optimal Biological Dose

Pharmacokinetic and pharmacodynamic data (i.e., peripheral blood and tumor/skin tissues) are being collected to inform on RO7296692 exposure-response relationship in order to select the optimal biological dose (OBD) required for RO7296682, which may be different from MTD.

4.3.3 Rationale for the Expansion Dose

The RO7296682 dose selected for Part II of BP42595 studying the combination of RO7296682 with atezolizumab is [REDACTED] mg Q3W.

This dose was selected based on the integration of all available safety, efficacy, PK, and PD data from Study WP41188. While there was neither correlation between drug concentration and clinical response (according to RECIST 1.1.) nor AEs (such as frequency of total reported, related, immune-mediated, and skin-related AEs), a dose-dependent effect on [REDACTED] was observed. Consequently, the dose recommendation is based on PK/PD modelling with an optimization towards [REDACTED] with the least possible effect on [REDACTED] in the periphery.

The anti-tumor activity observed in the first 10 response-evaluable participants with an [REDACTED], treated with [REDACTED] mg RO7296682 (and fixed dose of atezolizumab) will be assessed. If the ORR is less than 25%, another RO7296682 dose, which previously cleared in Part I may be explored. In this scenario the [REDACTED] mg dose cohort will be closed and a new Part II dose cohort will be initiated. The Sponsor is committed to action based upon emerging data and to aim at optimizing the dose

selection process in real-time which may include the exploration of other doses with an expected improved Benefit-Risk profile. To this end, a total of approximately 60 participants are planned to be enrolled in Part II.

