3. OBJECTIVES AND ENDPOINTS

The objectives and corresponding endpoints are provided in [Table 4](#).

Note: Due to the adaptive nature of Part III, additional cohorts, which are not described in this protocol, may be added in the study (see [Appendix 6](#), [Appendix 7](#), [Appendix 8](#), and [Appendix 9](#)). For a rationale, see [Appendix 9](#).

Table 4 Objectives and Endpoints

Objectives	Endpoints
Primary	
All Parts (Dose Escalation [Part I] and Dose Expansion [Part II and Part III])	
To evaluate the safety, tolerability, maximum tolerated dose (MTD) and/or recommended Phase 2 dose (RP2D) (Part I only) of RO7296682 when administered in combination with atezolizumab.	
 • Nature and frequency of adverse events (AEs) with severity determined according to NCI CTCAE v5.0 • Nature and frequency of dose-limiting toxicities (DLTs) in Part I
Primary (Dose Expansion Part II and Part III)	
To evaluate the preliminary anti-tumor activity of RO7296682 when administered in combination with atezolizumab.	
 • Objective response rate (ORR) according to RECIST v1.1
Secondary (Dose Escalation, Part I)	
To evaluate the preliminary anti-tumor activity of RO7296682 when administered in combination with atezolizumab.	
 • ORR according to RECIST v1.1
Secondary (Dose-Escalation [Part I] and Dose Expansion [Part II and Part III])	
To further characterize the anti-tumor activity of RO7296682 when administered in combination with atezolizumab.	
 • Disease control rate (DCR) defined as response rate (RR) and stable disease (SD) • Duration of response (DoR) • Progression-free survival (PFS) 
All according to RECIST v1.1
 
 • Overall survival (OS), if data are mature at the time of analysis
To investigate the pharmacokinetic (PK) profile of RO7296682 and atezolizumab after administration of RO7296682 in combination with atezolizumab.	
 • PK profiles and parameters derived for RO7296682 and atezolizumab, as appropriate, including but not limited to: 
 ○ Area under the curve (AUC) ○ Minimum (C_{\min}) and maximum (C_{\max}) concentration ○ Time of maximum concentration (T_{\max}) ○ Volume of distribution at steady-state (V_{ss}) ○ Half-life ($t_{1/2}$)

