9.2 SAMPLE SIZE DETERMINATION

Part I:

The maximum total number of participants in the dose escalation portions of Part I will be approximately 60 DLT-evaluable participants on a Q3W schedule. The exact sample size cannot be pre-determined and depends on the number of cohorts needed to reach

a MTD and/or RP2D. However, the simulations presented in Section 3 of [Appendix 11](#) show simulated sample sizes in a variety of toxicity scenarios.

Part II:

Approximately 60 CPI-experienced participants with NSCLC, HNSCC, and MEL will be enrolled in Part II in order to have around 10 participants per indication and aim for at least 30 response-evaluable participants with an ██████████, which is confirmed in the fresh baseline biopsy. With around 10 participants per indication, there will be sufficient number for decision making to open Part III cohorts ([Table 18](#)). Participants with MEL, NSCLC and HNSCC which are not amenable to standard treatment, will be enrolled in Part II; however, if emerging data suggest alternative indications should be pursued, then participants with ovarian, esophageal, TNBC or other indications as deemed fit may be considered.

Part III

In Part III, each tumor-specific cohort for NSCLC, HNSCC, and MEL may be opened for approximately 20 response-evaluable participants given that any of the gating criteria defined in [Section 9.5](#) are met based on the corresponding indication in single agent dose expansion of WP41188, Part I of this study, or Part II of this study. The futility interim analysis will be performed when the first 10 response-evaluable participants have mature data in each tumor-specific cohort. The detail of the futility analysis is provided in [Section 9.5](#).

For the CPI-experienced HNSCC cohort in Part III, the sample size of 20 response-evaluable participants allows to declare futility with a probability of 92% under the assumption that the true ORR is 5%, based on the posterior probability for ORR to be below 20% with a 70% confidence level.

For CPI-experienced NSCLC cohort in Part III, the sample size of 20 response-evaluable participants allows to declare futility with a probability of 87% chances under the assumption that the true ORR is 10%, based on the posterior probability for ORR to be below 25% with a 70% confidence level.

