9.4.2 Efficacy Analyses

The primary and secondary efficacy analyses listed in [Table 14](#) will include all participants in the efficacy population with participants grouped according to dose cohort (and schedule if applicable) within each study part.

Table 14 Efficacy Statistical Analysis Methods

Endpoint	Statistical Analysis Methods
According to RECIST Version 1.1 criteria (Appendix 13) and iRECIST (Appendix 14) 
• Objective response rate (ORR)• Disease control rate (DCR)• Duration of response (DoR)• On treatment progression free survival (PFS)	No formal statistical model and no formal hypothesis testing are planned in this study. Tumor response data will be reported using descriptive statistics. Response data will be listed. Participants with missing or no response assessments will be classified as not evaluable unless there is documented clinical deterioration, in which case participant will be classified as non-responders. Reasons for the non-evaluability will be summarized (e.g., withdrawal of consent, study discontinuation because of AE or physician decision). ORR and DCR will be summarized by using relative frequencies and 90% confidence interval (CI). Duration of response and PFS (on-treatment) will be summarized by using time-to-event analyses and Kaplan-Meier curves.
• Overall Survival (OS) (if available)	OS data may be tabulated and summarized using time-to-event analyses and Kaplan-Meier curves if data are collected and mature. Summaries will be carried out by cohort (and schedule if applicable) separately for each part.

Objective response rate (ORR) is determined as the rate of participants with an overall response of CR or PR. DCR is determined as the rate of participants with an overall response of either CR, PR, or SD rate. ORR and DCR will be derived for RECIST v1.1 and will be based on Investigators' assessment. Objective response (OR) is defined as a CR or PR as determined by the Investigator. For this protocol, confirmation of response is required at least 4 weeks after a first response occurred. To classify a response as SD, measurements will have to be classified as stable (according to RECIST v1.1) at least once after study entry at a minimum of 6 weeks after study entry. Participants with missing or no response assessments will be classified as not evaluable unless there is documented clinical deterioration, in which case participants will be classified as non-responders.

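### The 10 participants whose responses decide whether the Part II dose is kept also count in that dose's primary ORR, which is biased upward given retention to the extent the permissive rule is followed

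*Combined protocol and SAP*

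**What the plan says.** ORR by RECIST v1.1 is a primary endpoint in the expansion parts (Section 3, Table 4, "Primary (Dose Expansion Part II and Part III").

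Section 4.3.3 sets an early look at one named (redacted) dose. It concerns "The anti-tumor activity observed in the first 10 response-evaluable participants with an" eligible tumour phenotype (redacted). The rule is: "If the ORR is less than 25%, another RO7296682 dose, which previously cleared in Part I may be explored". If that option is taken, the current "dose cohort will be closed and a new Part II dose cohort will be initiated". The same section adds that "a total of approximately 60 participants are planned to be enrolled in Part II".

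Section 9.2 says Part II should "aim for at least 30 response-evaluable participants with an" eligible phenotype confirmed in the fresh baseline biopsy. That is a Part II aim and not a size for each dose.

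Section 9.4.2 takes the whole efficacy population, grouped by dose cohort within each part, and Table 14 states: "ORR and DCR will be summarized by using relative frequencies and 90% confidence interval (CI"). No interval method is named. The efficacy population in Table 13 does not set the first 10 aside. Section 9.5 (Interim Analyses) covers the criteria for opening Part III cohorts and Part III futility, and does not list this look. Section 9.1 plans no formal hypothesis test.

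**The concern.** The same responses serve twice: first to decide whether the dose cohort goes on, then as part of the estimate for the cohort that went on. When a low early count tends to close a cohort, the cohorts that survive are those whose first 10 did well, partly by chance. A plain proportion over all participants carries that chance excess forward, and an ordinary interval does not allow for it.

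No test is planned, so estimation is the whole efficacy output of Part II. Anyone reading the ORR of a dose that passed the check would read a figure that runs high, and nothing in the plan tells them so. No sentence states the re-use outright; it follows from the analysis-set wording in Section 9.4.2 and Table 13.

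**Working it through.** The plan gives no operating figure for this check, so there is none to reproduce.

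**Inputs from the documents.** Look at n = 10; threshold 25%, so 2/10 = 20% falls below it and 3/10 = 30% passes; about 60 participants in Part II; an aim of at least 30 phenotype-confirmed.

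**Assumptions.** (a) The rule is always followed, which makes the results upper bounds. (b) The retained dose ends with N = 30 or N = 60 response-evaluable participants; no per-dose size is stated. (c) The true ORR p is 10% to 40%. Section 9.2 gives no Part II value; for Part III it uses 5%, 10% and 15% as low-activity values. (d) The interval is Clopper-Pearson.

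**Formulas.** Let X1 ~ Bin(10, p) be responders among the first 10.
- P(kept) = P(X1 ≥ 3).
- Mean of the pooled ORR given kept = (E[X1 | X1 ≥ 3] + (N − 10)p) / N.

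**Worked case, p = 20%.**
- P(X1 = 0, 1, 2) = 0.1074, 0.2684, 0.3020, so P(kept) = 1 − 0.6778 = 0.3222.
- E[X1 | X1 ≥ 3] = (2 − 0.2684 − 2 × 0.3020) / 0.3222 = 1.1276 / 0.3222 = 3.50, so the first 10 average 35.0% in a kept dose.
- N = 30: (3.50 + 20 × 0.20) / 30 = 7.50 / 30 = 25.0%.
- N = 60: (3.50 + 50 × 0.20) / 60 = 13.50 / 60 = 22.5%.

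**All cases.**

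| True ORR | P(kept) | Mean in first 10 if kept | Pooled ORR, N = 30 (bias) | Pooled ORR, N = 60 (bias) |
|---|---|---|---|---|
| 10% | 7.0% | 32.1% | 17.4% (+7.4) | 13.7% (+3.7) |
| 20% | 32.2% | 35.0% | 25.0% (+5.0) | 22.5% (+2.5) |
| 30% | 61.7% | 39.1% | 33.0% (+3.0) | 31.5% (+1.5) |
| 40% | 83.3% | 44.6% | 41.6% (+1.6) | 40.8% (+0.8) |

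**Interval.** At p = 20% and N = 30, the lower 90% limit exceeds 20% from 11 responders upward. Without selection that has probability 2.6%. Jointly with X1 ≥ 3 it is 2.18%, so given retention it is 0.0218 / 0.3222 = 6.8%. At N = 60 the figures are 4.3% without selection and 9.0% given retention. Total coverage given retention is 93.2% (N = 30) and 90.7% (N = 60), so nearly all misses are on the high side. At p = 10% coverage falls to 82.5% and 85.4%. The method matters: a Wilson interval at p = 20% and N = 30 covers 85.0% given retention, against 89.5% without selection.

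**Averaged over kept and closed outcomes.** If a closed cohort stops at 10, the simple ORR of the first dose is biased downward: −3.2 points (N = 30) and −4.0 points (N = 60) at p = 20%.

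**Estimators.** The ordinary two-stage UMVUE is the expected first-stage rate given the total count. Given retention it therefore averages E[X1 | X1 ≥ 3] / 10 = 35.0% at p = 20%, worse than the pooled 25.0%. The rate in participants after the first 10 averages exactly p given retention. The conditionally unbiased version (UMVCUE, given at least 3/10) also averages p; it turns 8/30 (26.7%) into 22.3% and 15/60 (25.0%) into 22.8%.

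**The case against.** The strongest reply is that the rule does not bind. Another dose *may* be explored, so a dose with 0 to 2 of 10 can continue. A reader might infer that a retained dose always opens with at least 30% responders; the text does not support that. This stands, and it is why the figures are upper bounds. Looser use of the rule shrinks the bias but does not change its sign.

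A reader might also picture several doses tried in turn, each passing or failing the same check. Section 4.3.3 applies the check to one dose and mentions one new cohort. It does not say that the check repeats or how many doses may follow, so no figure for a sequence of doses belongs here.

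Third, 30 is not a per-dose size. If the first dose passes, most of the roughly 60 could go to it, and the N = 60 column is then the closer guide.

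Fourth, the consequences are limited. There is no formal test, so this is not a type I error problem. Part III cohorts open on per-indication response counts and enrol separately, so Part III ORR is untouched. Section 9.4.2 groups results by dose cohort, so a closed dose would be reported too. All of this stands. It lowers the weight of the point but does not remove it, because the plan describes neither the selection nor its effect on a primary endpoint.

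**Conclusion.** The point holds as a conditional one. Given that a dose is retained, and to the extent that the check is acted on, its pooled ORR runs high. The upper bounds are about 1 to 5 points for true ORRs of 20% to 40%. They reach 4 to 7 points at 10%, where a dose is kept only 7% of the time. At a true ORR of 20% the effect is a point estimate that is too high and misses shifted to one side; total coverage of an exact 90% interval does not fall below 90%.

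The documents do not support a claim that the estimate is biased upward overall: averaged over kept and closed outcomes it is not. The sizes rest on the four assumptions listed in the working, chiefly strict use of the rule and a final N between 30 and 60. This is a cheap reporting improvement and no reason to change the conduct of Part II.

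**What to change.** Leave the Section 4.3.3 dose check as it is. Add one paragraph to Section 9.4.2: for any Part II dose cohort continued after that check, report the ORR and 90% CI in participants enrolled after the first 10 next to the pooled ORR and its 90% CI, and state how many Part II dose cohorts were opened and closed.

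Do not use the ordinary two-stage UMVUE, since it increases the bias given retention. If an adjusted estimate is also wanted, use one that is conditionally unbiased given at least 3 of 10 (UMVCUE), as a supportive figure and only if the rule was in fact followed.

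The cost is a paragraph and minor programming. The added interval is wider: by about √(30/20) = 1.22 times if the dose reaches 30 participants and √(60/50) = 1.10 times if it reaches 60. On average the added figure will also be less favourable than the pooled one.
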